1. GENERAL QUESTIONS

Protocol Number [IRB-300007323](#)

Principal Investigator Name [[name]](#)

Title of proposed project:

[Ketone Monoester Supplementation in Cystic Fibrosis: A Pilot and Feasibility Study](#)

* Select the type of application you are submitting to the IRB for review. [Continuing Review](#)

NOTE: The ePortfolio should NOT be used for Continuing Reviews for protocols not INITIALLY submitted on the ePortfolio. [Please see instructions for submitting the appropriate form here.](#)

The OIRB has developed [a list of tips and best practices for IRB submissions](#). [Review the document here for assistance in developing your application.](#)

Initial IRB Protocol Application

* **PURPOSE:** In non-technical, lay language, provide the purpose of the project. The contents of this section are copied to other areas of IRAP. As such, provide **only** the purpose of the project here.

Assess the acceptability and tolerability of an exogenous ketone monoester supplement and determine its effects on reducing markers of inflammation in the lungs and improving clinical outcomes for patients with cystic fibrosis. The exogenous ketone that will be used in this study is a commercially available nutritional supplement known as KE4 from KetoneAid, Inc. Biomarkers of inflammation and nutrition will be analyzed in the blood and sputum samples.

BACKGROUND: In 2-3 paragraphs, summarize the past experimental/clinical findings leading to the design of this project. Include any past or current research that informed the study design and any previous results that are relevant to understanding the project. Lastly, list the study outcomes that will be measured to evaluate the purpose of the project. It is not necessary to include methodology in this section. NOTE: Technical terms must be defined in simple language. Abbreviations must be spelled out. Provide references for any specific citations.

Our group has investigated the physiological and metabolic responses to a number of exogenous ketone supplements in both rodents and humans. Our experience and that of our colleagues lead us to the conclusion that exogenous ketone supplements provide an exciting approach to increase circulating ketone concentrations. These findings suggest that administration of exogenous ketones might hold promise in reducing inflammation in a number of chronic disease conditions that cause inflammation, including CF.

METHODS: Describe the procedures for all aspects of your protocol. Tell us what you are doing.

Participants will be recruited by the Principal Investigator or Study Coordinator from the inpatient and **outpatient** CF population at UAB. Following admission to UAB Hospital for a routine CF exacerbation, **or within the outpatient setting**, the Study Coordinator will discuss the study with participants and obtain written informed consent before initiating the study.

Patients will be randomly allocated in unbalanced numbers (2:1) (n = 15 ketone and n = 8 control) to receive a ketone monoester or an identical-tasting placebo, respectively, for 8 days during the course of hospitalization for treatment of acute pulmonary exacerbation (One, 60 mL bottle of either a ketone ester will be consumed twice daily (30 mL or 15.0 g per dose) (KE4, KetoneAid, Falls Church, VA; 15.0 g or placebo (PL, flavored to closely match taste of the ketone) will be administered following an overnight fast and again at 1500h.

Participants will be **asked to drink about 1 fluid ounce of the ketone or placebo supplement twice a day (once in the morning and once mid-late afternoon) for up to 7 days. Each day in the study, the participant will be asked to fast overnight for about 8 hours before drinking the first dose of ketone or placebo. Following administration of the first dose of either the ketone or placebo and on either day 5, 6, or 7 a small drop of blood will be obtained from their finger before (time 0 min) and 15, 30, 60, 90, and 120 min after drinking the supplement. On days in between visit 1 and visit 2, we will check their blood sugar before drinking the supplement and 30 minutes after they drink the supplement. We will use a commercially available ketone meter (Keto-Mojo, Napa, CA) that provides a rapid assessment of blood ketone and glucose (sugar) levels. The Keto-Mojo device requires a finger stick with a lancet, identical to those used to measure blood sugar, and uses only a small drop of blood. Patients will be educated on how to use the device and self measure ketone and blood sugar.**

Blood sampling will occur from their indwelling catheter or **venipuncture** at day 1 and at day 5, 6, or 7 before administration of the ketone or placebo. We will try to coordinate this with any blood sampling done for clinical care.

The Keto-Mojo device requires a finger stick with a lancet, identical to those used to measure blood sugar, and uses only a small drop of blood. The device provides values within about 15 seconds following sampling. An alcohol prep will be used to cleanse the surface of the skin prior to each stick and a bandage will be applied to reduce risk of infection.

Participants will remain on all CF chronic care medications **and/or** standard exacerbation therapy (intravenous antibiotics and increased airway clearance throughout the course of the study. The study pharmacist will provide the ketone or placebo supplements by computer-generated random assignment in blocks of three participants and will have sole access to the randomization code.

Spirometry measurements, CRP, and, history/physical exam and Sputum bacteriology will be conducted at the beginning of hospitalization as part of standard of care (these results will be pulled from the medical record for study purposes. Spirometry measurements and history/physical exams will also be performed at the end of hospitalization as part of standard of care and will be pulled from the medical record for study purposes.

For outpatient subjects, these results will be pulled from the medical record and study procedures will also be performed at visit 1 and visit 2 as according to the consent

Spirometry will also be performed in addition to those for standard care just before the participant drinks the ketone supplement or placebo control and one hour after on day 1 and either day 5, 6 or 7.

Additional sputum and blood will be collected at baseline before the treatment and at patient-discharge for trial-specific readouts.

The participants will also be asked to complete the CFQR questionnaire and a food diary every night. They will also be asked to complete the symptom questionnaire on hour after receiving the morning ketone or placebo.

REQUIRED - SELECT ONE OR BOTH: Will this be a retrospective study and/or a prospective study?

Yes No * Retrospective

Yes No * Prospective

Yes No * Will the study involve the prospective collection or analysis of data, documents, or records?

Yes No * Will the study involve the prospective collection or analysis of biospecimens?

What is the expected end date of the study (including data analysis)?

* Provide the total number of subjects to be included at all sites, both retrospectively (including records) and prospectively.

* Provide the total number of subjects to be included at UAB, both retrospectively (including records) and prospectively.

Select the status of the Principal Investigator.

Faculty/Staff

Student/Trainee

Yes No Are any of the investigators listed on the IRB Personnel Form students using this research for their capstone project, thesis, or dissertation?

Yes No Is the project to be conducted internationally?

Procedure List

Select all study procedures and indicate whether the procedures are research only or routine.

Procedure	Select whether the procedure is research or routine.	
Blood drawing	Protocol Driven	
Biological sampling (other than blood)	Protocol Driven	
Placebo	Protocol Driven	
Randomization	Protocol Driven	
Pregnancy testing	Protocol Driven	
Record review (which may include PHI)	Protocol Driven	
Placebo	Protocol Driven	
Physical Exam	Protocol Driven	
Surveys, questionnaires, or interviews (one-on-one)	Protocol Driven	
Diet, exercise, or sleep modifications	Protocol Driven	
Food supplements	Protocol Driven	

Yes No Does the protocol involve any procedures not described in the above table?

Describe the procedure(s), including whether the procedure(s) are research only or routine.

spirometry- protocol driven

Research Area

Select the type of research.

Biomedical (non-oncology)

Behavioral (non-oncology)

Oncology

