This randomized controlled trial (RCT) aims to evaluate the effectiveness of a commercially available ketone supplement on pulmonary function and markers of inflammation and metabolic health in patients with cystic fibrosis (CF) admitted for acute pulmonary exacerbation and a cohort of stable outpatient CF subjects. To accomplish this goal, a 5-7 day RCT will be conducted to compare the effects of ketone supplementation to a placebo control. The primary outcome will be differences in pulmonary function, namely FEV1.0, FVC, and FEV1.0/FVC. Secondary outcomes will include quantitative assessment of circulating insulin, glucose, and a number of inflammatory markers associated with the NLRP3 inflammasome. Qualitative assessment of tolerability and the feasibility of delivery will also be extensively examined. Compared to placebo control and standard care, we hypothesize that the ketone ester (KE4, KetoneAid, Falls Church, VA) will produce greater reductions in markers of inflammation and improvements in pulmonary function. We further hypothesize that ketone supplementation will be well-tolerated and prove to be feasible as it relates to administration and consumption of the ketone. Of note, this Ketone supplement is considered GRAS and does not require FDA IND or FDA oversight.

The intervention and measurement protocols pose minimal risk to participants (as described below). Because of this low-risk status, the data safety monitoring plan (DSMP) for this trial focuses on close oversight by Medical Monitor, [name]. We will also provide prompt reporting of excessive adverse events and any serious adverse events to the Cystic Fibrosis Center, IRB at the University of Alabama at Birmingham (UAB) and NIH. The data safety monitoring plan (DSMP) outlined below will adhere to the protocol approved by the UAB IRB.

Safety reports will be sent to the study statistician, the MPIs, and to medical oversight at the schedule specified below in the table. The project coordinator will be responsible for assembling the data and producing these reports, as well as assuring that all parties obtain copies of these reports. The frequency of data review for this study differs according to the type of data and can be summarized in the following table:

Data type	Frequency of review
Subject accrual (adherence to protocol regarding demographics, inclusion/exclusion)	After every 5 patients that complete the study

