Once randomized participants begin the intervention, data on treatment adherence will be monitored by research staff on an ongoing basis. Adherence will be measured as the number of times the participant consumes the placebo or ketone supplement. Adherence will be reviewed after every 5 participants or quarterly (whichever comes first) and if the safety officer has concerns about whether compliance has reached a level that might inhibit the ability of the study to test its primary hypotheses, he will suggest a conference call for study investigators to discuss methods for improving compliance.

Statistical analyses and stopping rules

Although no formal power analysis was conducted for this study (due to exploratory nature of the study as pilot and feasibility), our 2:1 (ketone:placebo) recruitment strategy will provide opportunity to detect smaller differences in the ketone treated group. We plan for no interim efficacy analyses and will not unblind until recruitment is complete. In this minimal-risk study, it is more likely that drop-outs or difficulty in recruiting adequate numbers of participants will require stopping the trial than that excess adverse events will occur and require stopping the trial. However, as outlined elsewhere, we will monitor adverse event rates in all participants and aggregate by randomized group. The safety officer, together with the PI, will alert the UAB IRB and the NIH if a larger than reasonably expected adverse event rate should occur in either treatment condition. Other issues relating to stopping rules for this trial include:

New Information

It is exceedingly unlikely that any new information will become available during this trial that would necessitate stopping the trial.

Limits of Assumptions

It is possible that baseline differences between the groups, excessive study dropouts, and/or missing data by the interim measurement time points will limit the value of data analysis of measurements. Baseline differences will be evaluated and effects on the power to detect differences in the primary outcome will be evaluated and communicated to the PIs, and safety office. Given the monitoring plans outlined elsewhere in this document as well as the randomized design of this study, it is exceedingly unlikely that there will be baseline differences between groups of any magnitude to threaten the validity of the study.

Limits of Rules

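### The bottle phrase in the dosing sentence contradicts its own per-dose figure, and the 8-day course conflicts with a course of at most 7 days stated elsewhere

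*Protocol*

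**What the plan says.** **Amount.** Section 1 (General Questions), Methods, gives the intake as "One, 60 mL bottle of either a ketone ester will be consumed twice daily (30 mL or 15.0 g per dose". The same sentence then repeats 15.0 g and says that the product "will be administered following an overnight fast and again at 1500h". In the next paragraph participants are "asked to drink about 1 fluid ounce of the ketone or placebo supplement twice a day".

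**Duration.** The first of these two paragraphs gives treatment "for 8 days during the course of hospitalization for treatment of acute pulmonary exacerbation". The second gives it as "once in the morning and once mid-late afternoon) for up to 7 days". The DSMP (Appendix 9, Introduction) says that "a 5-7 day RCT will be conducted to compare the effects of ketone supplementation to a placebo control", and it describes the trial as covering both patients admitted for exacerbation and stable outpatients. The time-commitment answer in section 9 (Prospective) gives 7 days of data collection, and the recruitment flyer (Appendix 8) calls it a 7-day study. The second finger-stick series, blood sample and additional spirometry are placed on day 5, 6 or 7.

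**Adherence.** The DSMP states: "Adherence will be measured as the number of times the participant consumes the placebo or ketone supplement".

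**The concern.** The amount taken and the number of days together define the intervention, and the Methods section is the only place in the protocol that gives a volume or gram amount. Its main sentence contains a phrase that, taken alone, doubles the dose in its own bracket.

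Little else in the protocol would catch a misreading. The storage and dispensing plan in the Drug Review Sheet gives no volume, bottles per day or bottles per participant. The data sheet in Appendix 2 has no field for volume taken. Adherence counts intakes, so a 30 mL intake and a 60 mL intake score the same.

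The duration conflict has its own consequences. It changes total exposure and the number of planned doses against which a count of intakes is judged. It also decides whether the second assessment falls at the end of treatment or part-way through it. Tolerability and feasibility are stated aims, and the safety officer is asked to judge whether compliance is high enough to test the primary hypotheses. Both need a known planned course.

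**Working it through.** **Inputs, all from the protocol**
- Section 1, Methods: 60 mL bottle; 30 mL or 15.0 g per dose; two intakes a day; about 1 fluid ounce per intake; 8 days; up to 7 days; second assessment on day 5, 6 or 7.
- Appendix 9: 5-7 days. Section 9 and Appendix 8: 7 days.
- The one outside figure is the unit conversion 1 US fluid ounce = 29.57 mL.

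**Step 1: do the per-dose figures agree?**
- Concentration = 15.0 g / 30 mL = 0.5 g/mL.
- Bracket: 30 mL × 2 = 60 mL a day; 60 × 0.5 = 30 g a day. That is exactly one 60 mL bottle a day.
- Fluid-ounce text: 29.57 mL × 2 = 59.1 mL a day; 59.1 × 0.5 = 29.6 g a day. The per-dose difference from 30 mL is (30 − 29.57) / 30 = 1.4%, well within the word *about*.

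The per-dose figures therefore agree with each other.

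**Step 2: the bottle phrase read literally**
- 60 mL × 2 = 120 mL a day; 120 × 0.5 = 60 g a day.
- Ratio to the bracket: 120 / 60 = 2.0.

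**Step 3: durations side by side**

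| Place | Stated length |
|---|---|
| Section 1, Methods, first dosing paragraph | 8 days |
| Section 1, Methods, next paragraph | up to 7 days |
| Section 9, time commitment | 7 days |
| Appendix 8, flyer | 7 days |
| Appendix 9, DSMP Introduction | 5-7 days |

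The last four fit one flexible window that ends no later than day 7. The 8-day figure does not.

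**Step 4: what the days change.** This uses the per-dose figure and assumes two intakes on every day of the course.

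| Days | Planned doses (2 × days) | Total intake (30 g × days) |
|---|---|---|
| 5 | 10 | 150 g |
| 7 | 14 | 210 g |
| 8 | 16 | 240 g |

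- 8 against 7 days: 240 / 210 = 1.14, or 14% more.
- 8 against 5 days: 240 / 150 = 1.60, or 60% more.
- A participant with 14 recorded intakes has completed a 7-day course (14/14) but only 14/16 = 87.5% of an 8-day course.
- In an 8-day course, the second assessment on day 5, 6 or 7 falls 8 − 7 = 1 to 8 − 5 = 3 days before the last day. In a 5-7 day course it can coincide with the last day.

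The number of days changes total exposure and the planned count. It does not change the daily amount.

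**The case against.** The strongest reply is that a careful reader is not misled about the amount. The bracket, the repeated 15.0 g and the fluid-ounce text all agree, and two 30 mL doses empty one 60 mL bottle exactly. This stands. A reader might infer from the bottle phrase that the daily amount is open by a factor of two, and multiply through to 60 g × 8 days = 480 g. The documents do not support that, because it means setting aside every per-dose figure they give.

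A reader might also infer that dose is confounded with setting, since inpatients are supplied by the research pharmacy and outpatients by research staff. That too is unsupported. The dispensing plan states no volume, and nothing shows that the two routes would read the sentence differently.

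On duration, four of the five statements can be reconciled as one window capped at day 7. This also stands, and it narrows the conflict to the 8-day figure. One might answer that 8 days applies only to inpatients, because that sentence concerns hospitalization. But no passage sets separate durations by setting, and the DSMP gives 5-7 days for a trial covering both groups.

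On adherence, the protocol defines a count, with no percentage or threshold, and an analysis plan that was not available may set one. The absence of a percentage is therefore no fault. What remains is that the planned count itself depends on which stated duration applies.

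**Conclusion.** Two contradictions in the text that defines the intervention hold.

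1. The bottle phrase, read literally, is 2.0 times the per-dose figure in its own bracket. It is a wording error beside per-dose figures that agree with each other, and it does not leave the daily amount open.
2. A course of 8 days cannot be squared with up to 7 days in the next paragraph or 5-7 days in the DSMP. The size is 14% in total intake for 8 against 7 days and 60% for 8 against 5 days, with 10, 14 or 16 planned doses. It also leaves unclear whether the second assessment marks the end of treatment.

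The totals assume the stated per-dose figure and two intakes on every day. Nothing in the documents shows that any participant received a wrong amount. The point should be corrected, but it does not undermine the design.

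**What to change.** The sponsor must reconcile these passages. This review does not say which dose or duration is right.

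- Reword the bottle phrase so that it matches the per-dose amount intended, giving the volume and grams per intake, the daily total, and the number of bottles that this represents.
- State one planned duration, or one window with the rule that decides each participant's last day, in the same words in the Methods, the dispensing plan in the Drug Review Sheet and the DSMP. Bring section 9 and the flyer into line.
- Count adherence against each participant's planned doses under that duration or window.
- Say how the day 5, 6 or 7 assessment relates to the last day of the course.

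The cost is wording in one amendment. No procedure, visit or sample needs to be added.

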12. DEVICES

- Comparison
- Randomized
- Open Label
- Control
- Other
- Yes No * Is the trial blinded?
- * Is the trial single or double blinded? [Double Blinded](#)

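### Ketone readings are taken before the one-hour assessments with no masking described, and the protocol contradicts itself on who holds the meter

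*Protocol*

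**What the plan says.** **Blinding.** Protocol section 12 (Devices) declares the trial "double blinded". The data safety monitoring plan (section 31, Appendix 9, statistical analyses and stopping rules) adds that the team "will not unblind until recruitment is complete".

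**Readings.** Under section 1 (Methods), finger sticks on day 1 and on day 5, 6 or 7 are taken before the dose and "15, 30, 60, 90, and 120 min after drinking the supplement". The meter reports ketones and glucose: "The device provides values within about 15 seconds following sampling". The Methods then say "Patients will be educated on how to use the device and self measure ketone and blood sugar". On the days between the two visits the scheduled check is blood sugar, before and 30 minutes after the supplement.

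**Assessments.** The Methods add study spirometry before the dose and one hour after it on the same two days. The symptom form is due one hour after the morning dose, and the CFQ-R and food diary are completed at night.

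**Who has the meter.** The Device Review Sheet says that the research coordinator keeps the meter and that it does not go to patients.

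**Who has the code.** The Methods give the study pharmacist alone access to the randomization code. The Drug Review Sheet has the principal investigator store and dispense outpatient product, described as blinded, according to that code. On safety tables Appendix 9 says "we will monitor adverse event rates in all participants and aggregate by randomized group". It also says "The project coordinator will be responsible for assembling the data and producing these reports" and "Safety reports will be sent to the study statistician, the MPIs, and to medical oversight".

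**The concern.** A matched taste and a blinded supply protect against recognising the product. They do not protect against a meter that displays, within seconds, the analyte the product is meant to raise. If the procedures are followed as written, someone the blind should cover can see a value that points to the arm before the one-hour assessments.

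What is at stake differs by outcome. CFQ-R and the symptom form are self-reported and open to expectation. Spirometry, the primary outcome in Appendix 9, depends on effort and coaching. Section 2 (Continuing Review) already reports a perceived respiratory improvement on the CFQ-R, without saying whether it is a difference between arms. If participants could see their ketone values, such a gain could not be separated from expectation. Section 9 says the pilot is to supply preliminary data for an extramural grant, so this distinction will matter to whoever reads the results.

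**Working it through.** The plan states no figure to reproduce: Appendix 9 says no formal power analysis was done. The check is one of timing and consistency.

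**1. Order of events on each series day (section 1, Methods).**
- Post-dose readings fall at 15, 30, 60, 90 and 120 min: 5 per day × 2 days = 10 per participant.
- One-hour spirometry and the symptom form fall at 60 min. Readings clearly before them are at 15 and 30 min: 2 per day × 2 days = 4. Whether the 60-min reading comes before or after them is not stated.
- If the CFQ-R is read as a nightly form, it follows all five post-dose readings on a series day.

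**2. Does a reading carry information on the arm?** Section 2 reports that the ester raised circulating ketones, but gives direction only. Accuracy of inference therefore cannot be computed. It could lie anywhere from that of always guessing ketone, 15/23 = 65.2%, to 100%.

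**3. Who sees the value?**

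| Reading of the protocol | Source | Person exposed |
|---|---|---|
| Patients are taught to test themselves for ketones and glucose | Section 1, Methods | The participant, who self-reports CFQ-R and symptoms |
| Coordinator keeps the meter; patients do not receive it | Device Review Sheet | The coordinator, if this is the study coordinator who collects all data (Appendix 9) |

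An inpatient could be taught to test on a meter the coordinator brings, so the two statements can be partly squared. For outpatients they cannot. Section 9 gives two visits over seven days, and the Methods schedule checks on the days between, which a meter that is never handed out cannot serve unless staff see the patient on those days. The scheduled between-visit test is glucose, so ketone exposure on those days depends on the self-measurement sentence.

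**4. Recording.** The data sheet in Appendix 2 carries BHB (the ketone value) and FEV1, FVC and FEV1/FVC together. Whoever enters spirometry on it has the ketone values in view.

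**5. The code.** Sole access by the pharmacist and dispensing by the investigator according to the code conflict in wording. Product already blinded and numbered by participant would satisfy both.

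**6. Reference for the arm guess.** Appendix 6 asks participants on the final day which arm they think they had. With 15 ketone and 8 control planned, always answering ketone is right for 15/23 = 65%, so 50% is not the benchmark. That strategy is right for everyone on ketone and no one on placebo, which is why the guess must be shown by arm.

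**The case against.** **Silence is not disclosure.** No sentence says that a blinded person is shown ketone values. This stands as a limit: the supportable statement is that no masking is described. But teaching patients to measure their own ketones goes beyond silence, and procedures for keeping the blind belong in a protocol.

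**The route to the primary outcome is weak.** A reader might infer that the coordinator runs spirometry knowing the arm. The documents do not support that. The operator is not named, and the response to the IRB in Appendix 3 includes respiratory therapists among the study staff. Nor is it stated whether the added sessions or the standard-of-care sessions supply the primary outcome. Section 2 reports no significant spirometry effect, so it gives no sign of bias there.

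**Roles may differ.** The titles research coordinator, project coordinator and study coordinator appear in different places and need not be one person. Consent may also be taken by other trained staff. Exposure of the person who collects data is therefore conditional.

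**The code and the safety tables.** A reader might infer that the investigator or coordinator knows the arms. That does not follow. The manufacturer supplies blinded product, and adverse events can be tabulated under masked group labels. These are points of wording.

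**CFQ-R is not a named outcome.** Appendix 9 lists neither CFQ-R nor the symptom form among the quantitative primary and secondary outcomes, although tolerability is to be examined. This limits the consequence. It does not remove it, because section 2 already reports a CFQ-R result.

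**Predicting later assignments.** A reader might infer that visible readings make the blocks of three predictable. With every earlier arm and the block position known, best guessing gives 2/3 + 2/3 + 1 = 7/3 correct per block against 2 for always guessing ketone. Over the 7 full blocks in 23 patients that gains 7 × 1/3 = 2.33 patients. This is an upper limit, and the documents do not show that its conditions are met. It is secondary.

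**Conclusion.** The point holds in limited form and should be fixed. The protocol promises a double blind, schedules ten post-dose ketone readings per participant with four of them clearly before the one-hour assessments, describes no masking, and contradicts itself on who holds the meter. Taken as written, the Methods expose the participant. The Device Review Sheet exposes a coordinator, who may or may not collect the outcomes.

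The most direct risk is to CFQ-R and symptom reports. For spirometry the risk is possible and not shown. The documents do not establish that the blind was broken for anyone.

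The conclusion assumes that readings are seen as they are taken, because nothing says otherwise, and that the ketone rise is large enough to notice, for which no magnitude is given. Enrolment status is not legible in this copy.

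**What to change.** For any remaining enrolment:

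- **(a) Meter.** Reconcile section 1 (Methods) with the Device Review Sheet on who holds and reads it, separately for inpatients and outpatients.
- **(b) Masking.** Do not show ketone values to participants or to whoever coaches spirometry or administers questionnaires. Use existing staff. Leave glucose checks unchanged and keep the Medical Monitor's access.
- **(c) Recording.** Put BHB on a sheet separate from FEV1 and FVC, and restrict the BHB database fields until recruitment is complete.
- **(d) Code and tables.** State that the investigator handles only participant-numbered product, and that adverse event tables by group use masked labels.

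In all cases:

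- **(e) Reporting.** Give the final-day arm guess by arm, read against the 65% reference. State as a limitation, when interpreting CFQ-R, symptoms and spirometry, that no masking of ketone values was specified.

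If enrolment is closed, only (e) applies; patients already treated cannot be protected retrospectively.

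The cost is protocol wording, a split form, database permissions and some reassignment of tasks. Appendix 9 now limits data access to the investigator and study coordinator, so that sentence needs amending if someone else enters BHB. The documents tie no safety action to a ketone value, and the hypoglycemia contact is untouched. Glucose remains a small residual cue, since Appendix 9 expects a fall of no more than 5-7%. The arm guess covers participants only and detects loss of the blind without preventing it.
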